## 9.0 MONITORING UNTOWARD EFFECTS ASSOCIATED WITH OR RESULTING FROM STUDY

The study will have study clinicians prescribing FDA-approved oral PrEP, in accordance with Gilead's label indications for tenofovir disoproxil fumarate/ emtricitabine (Truvada) or emtricitabine/ tenofovir alafenamide (Descovy). The prescription of PrEP in the study will also follow guidance from the US Public Health Service and US Centers for Disease Control and Prevention. The study will not be providing study drug. Individuals will be getting prescribed medications from a local pharmacy. Side effects due to the medication will be monitored but not considered study-related adverse events.

The frequency and severity of side effects from Truvada and Descovy are listed as follows (items in bold are from the package insert):

- *Very Common (approximate incidence > 50%):* none
- *Common (approximate incidence > 25 - 50%):* none
- *Likely (approximate incidence of > 10 - 25%) and Mild to Moderate (no disruption to temporary interference with daily activities; may include prescription intervention):* **nausea, fatigue, headache, dizziness, depression, insomnia, abnormal dreams, and rash.**
- *Infrequent (approximate incidence of > 1 - 10%) and Mild to Moderate (temporary interference with daily activities; may include prescription intervention) :* **diarrhea, abdominal pain, decrease in weight**, generalized weakness, shortness of breath, increased cough, runny nose, allergic reaction, skin darkening of the palms of hands and/or soles of feet, muscle pain and weakness.
- *Rare (approximate incidence < 1%) and Severe to Life threatening: bone pain and bone changes,* worsening or new kidney damage or failure, liver problems, increases in pancreatic enzyme, increased triglycerides, increased creatine phosphokinase (CPK) which could mean muscle damage, lactic acidosis and severe hepatomegaly with steatosis that may result in liver failure

Site staff must first follow their own IRB's procedure for reporting and managing untoward effects.

There are two types of untoward effects to be identified: (1) those related to the participant and (2) those related to the study staff.

First, the study will catalogue any untoward effect related to the participant. All adverse events (AE) reported will be assessed by the PI for the study site in which the participant was enrolled for the severity, expectedness and relatedness. Reporting is required for occurrences including social harms, psychological distress and serious life-threatening events such as suicide attempts. These may be immediately apparent to the study staff, such as the participant's emotional upset requiring referral for counseling; or they may be delayed and reported later to study staff, such as physical harm to an individual for having participated in the study. Study staff will notify the team of these untoward effects using the iTech Query and Notification System (QNS) accessible through the iTech website (<https://itechnetwork.org>).

Serious adverse events (SAE) will be adverse events that result in death, are life threatening, requires or prolongs hospitalization, causes disability, or poses other significant hazards. Severity of AEs will be classified as follows: mild, moderate, and severe. Mild AEs will be events that do not require medical attention and are easily tolerated. Moderate AEs will be events that require simple and routine medical treatment and may cause some interruption to daily life. SAEs will be defined as above. AEs will also be categorized as definitely, possibly, or not related to the study. AEs that are definitely related will follow a logical causal sequence from a study activity. Possibly related events will follow a logical causal sequence from a study activity but may also be due to non-study activities. Not related events will be events that do not follow a logical causal sequence from any study activity. All adverse events require reporting to the ATN via the iTech Query system within 24 hours of becoming aware of the adverse event. Study staff will be briefed during the training on the scope of possible untoward effects and instructed to report events.

Second, study staff may encounter untoward events during virtual visits that personally affect them. Training and guidance will seek to minimize this risk. The protocol chairs should be notified of these events so that they may be immediately addressed, evaluated, and guidance modified or expanded to minimize similar risk to other staff.

A Safety Monitoring Committee (SMC) will receive standard data reports on a quarterly basis. The chair of the SMC will lead biannual calls to discuss study progress, and convene additional SMC meetings as needed based on interim reporting. The SMC will be tasked with stopping the study if the intervention proves to be significantly outperforming the standard of care, or if the inverse occurs. We will conduct one interim analysis comparing the efficacy of the intervention in the active arm to the control arm, with efficacy based on differences in trial success versus failure using the primary outcome definition (detectable Tenofovir at 12 months). We will use the O'Brien-Flemming spending function on the Z test statistic assuming a final alpha of 0.05 such that the interim Z statistic bounds are -2.96 and 2.96. If the intervention efficacy is outside those bounds, the trial will be stopped. If the intervention is significantly outperforming the standard of care, the study will seek to adjust study design and supplements to open the intervention arm. The SMC will monitor several other factors, including HIV seroconversion, changes in kidney function, behavioral disinhibition, medication adherence, persistence in PrEP care, and differential loss to follow-up.

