### 3.2 Sample Size

240 total participants, with 120 assigned to intervention and 120 assigned to control.

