## 8.4 Criteria for Premature Study Discontinuation

Participants may voluntarily withdraw from the study for any reason at any time. No further data collection will occur from the date the decision is made to permanently discontinue the subject from the study. The study investigators also may withdraw participants from the study in order to protect participant or staff safety. Study staff will record the reasons for all withdrawals. Early study discontinuation may occur for the following reasons:

- Participant has a confirmed HIV-positive test

- If the study is terminated prior to its planned end date
- If the study clinician or the PI determines it is in the participant's best interest to discontinue participation in the study
- If a participant threatens study staff

Any unexpected adverse events that meet the new safety information reporting criteria will be immediately reported to the UNC-CH IRB and the respective sites' IRBs if applicable. Study staff will complete a Study Stop form for participants who are discontinued. This form will include the date, last virtual visit completed, and reason for study discontinuation.

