## 10.2 Power Estimates

10.2.1 All analyses will assume 80% power to detect a difference at a two-sided 5% significance level. We will also assume a 20% attrition rate in both arms, with independent censoring. Assuming that 5% of participants in the control arm are above cut-point levels of the outcome measure (Section 10.1.2), we will have sufficient power to detect a minimum detectable effect size of 13% absolute difference in the outcome measure (e.g.  $\geq 18\%$  of participants in the intervention arm have outcome measures above the cut-point threshold). A sensitivity analysis determined that to allow for detection of a scenario where intervention outcome level = control+20% absolute increase, our study would remain sufficiently powered with any control participant uptake level  $\leq 15\%$ .

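### If the interim bound is crossed, the plan leaves unclear whether participants short of month 12 keep giving outcome data; losing them would leave an exaggerated and imprecise estimate

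*Combined protocol and SAP*

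**What the plan says.** Section 9.0 gives the Safety Monitoring Committee one interim efficacy comparison based on the month-12 outcome, with an O'Brien-Fleming-type bound of 2.96 in either direction. The action is unconditional: "If the intervention efficacy is outside those bounds, the trial will be stopped". If the intervention is ahead, the same section adds that "the study will seek to adjust study design and supplements to open the intervention arm".

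Section 8.4 lists reasons for early discontinuation, one of which is "If the study is terminated prior to its planned end date". It also says "No further data collection will occur from the date the decision is made to permanently discontinue the subject from the study".

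Section 8.1 plans 12 months of follow-up for all participants whether or not they take PrEP, with surveys every three months and DBS cards at months 6 and 12. Section 10.1.2 places the primary outcome at month 12 only. No section says what follow-up takes place after an interim stop, when the look happens, or how the effect would be estimated after a stop.

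**The concern.** The primary outcome takes 12 months to observe, so at the look some participants may be randomised but not yet at month 12. If a stop is treated as study termination under section 8.4, they give no month-12 card and have no primary outcome.

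Two things are then at stake. First, a trial that stops at a high bound does so partly because its interim data happened to be favourable, so the difference reported at the stop overstates the truth on average. The size of that difference is the plan's stated efficacy measure, and the interim test does not settle it. Second, precision falls, and the persistence, subgroup, mediator and cost-effectiveness analyses lose the month-12 data of those participants. A sample not taken at month 12 cannot be recovered later.

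If the intervention arm is opened instead, the plan does not say how to treat month-12 outcomes from controls who have by then gained access to ePrEP.

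**Working it through.** **Inputs**
- Section 3.2: "240 total participants, with 120 assigned to intervention and 120 assigned to control".
- Section 10.2.1, on error rates: "All analyses will assume 80% power to detect a difference at a two-sided 5% significance level".
- The same section, on loss to follow-up: "We will also assume a 20% attrition rate in both arms, with independent censoring". Expected month-12 outcomes are 120 × 0.8 = 96 per arm.
- Section 10.2.1, on the control rate: "Assuming that 5% of participants in the control arm are above cut-point levels of the outcome measure"; the detectable difference is 13 points, so 5% v 18%. Its sensitivity scenario is control plus 20 points with control up to 15%, so 5% v 25% and 15% v 35% are used as well.
- Section 9.0: bound 2.96.
- Not given: timing of the look and accrual rate.
- Assumption: the rates in section 10.2.1 (above the cut point) apply to the interim outcome. Section 9.0 describes that outcome as detectable drug, for which no rates are given.

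**The plan's own figures.** A two-sided 5% test of two proportions with 96 per arm has 81.1% power for 5% v 18%. The requirement is 94 per arm, and 94/0.8 = 117.5, or 118, against 120 planned. The power statement reproduces.

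**Where the look falls.** O'Brien-Fleming-type spending with 0.025 per side is α(t) = 2 − 2Φ(2.241/√t). At t = 0.5, α = 0.00153 and the bound is z = 2.963, which matches 2.96. Half of 96 is 48 per arm. If the two-sided 0.05 is spent directly, 2.96 corresponds to t of about 0.44.

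**Smallest difference that can cross at 48 per arm (pooled z).** With 0/48 control successes, 9/48 are needed, a difference of 18.75 points. With 2/48, 13/48 are needed (22.9 points, z = 3.09). If the truth is 13 points, every trial stopped for benefit overstates it.

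**Mean estimate given a stop for benefit.** This is exact binomial enumeration at 48 per arm; simulation of 1,000,000 trials agreed for the first three rows. The last column adds 48 unselected outcomes per arm, so it is (estimate at stop + true difference)/2.

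| True rates | Chance of stop | True difference | Mean at stop | Mean after completion |
|---|---|---|---|---|
| 5% v 18% | 12.0% | 13 | 23.4 | 18.2 |
| 5% v 25% | 39.6% | 20 | 26.6 | 23.3 |
| 15% v 35% | 23.1% | 20 | 31.1 | 25.6 |
| 5% v 40% | 92.4% | 35 | 36.2 | 35.6 |

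At 5% v 18% the excess falls from 10.4 to 5.2 points, which is half. The other half stays because the interim data remain in the estimate.

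**Sensitivity to the time of the look, bound held at 2.96, 5% v 18%.** At 36 per arm the mean at the stop is 26.6 points (chance of stopping 7.0%); at 72 per arm it is 18.8 points (29.5%).

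**Precision.** The 95% half-width is 1.96 × √[(p₁(1−p₁) + p₂(1−p₂))/n]. At 5% v 25%: 1.96 × √(0.235/48) = 13.7 points and 1.96 × √(0.235/96) = 9.7 points. At 5% v 18%: 12.5 and 8.8 points.

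**If controls gain access before month 12.** Take the extreme in which the later controls match the intervention rate, so the second half shows no difference. The pooled mean is (23.4 + 0)/2 = 11.7 against a true 13, or (26.6 + 0)/2 = 13.3 against a true 20. Completion then biases the estimate downward.

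**Over all trials, stopped or not.** The mean estimate is 13.6 against 13.0 at 5% v 18%.

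**The case against.** A reader might infer that the plan orders data collection to end at the stop. The documents do not say so. Section 9.0 stops the trial without mentioning data collection. The sentence in section 8.4 on no further data follows a sentence on voluntary withdrawal and concerns an individual participant, and the list that includes study termination is introduced permissively. Section 8.1 plans 12 months for all, and opening the intervention arm implies that participation continues. This part of the objection stands: the loss is a possible reading of two sections together. The ambiguity remains, because no section says that follow-up survives a stop.

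A reader might also infer that half the data behind every aim would go. That is not supported either. Surveys and month-6 cards already collected are kept, and month-12 cards stored for batch testing (section 5.5.4) can still be assayed. Nor do the documents show how many outstanding participants would already be randomised at the look; if few are, little is lost and little can be recovered.

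Finally, overestimation after an efficacy stop is a general property of such designs, is nearly absent if the true effect is about 35 points, and is small when averaged over all trials. All of that is correct. It limits the size of the point but does not remove the need to say what happens to participants already randomised.

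**Conclusion.** The point holds as a gap to close, and closing it is a cheap improvement. Sections 9.0, 8.4 and 8.1 allow opposite readings of what happens to participants short of month 12 after a stop, and they must be reconciled.

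The size is conditional on a stop for benefit. With the look at about half the information, the overstatement averages about 10 points when the truth is the planned 13, and about 7 points when the truth is 20 from a 5% control rate. Completing follow-up would remove about half of this and restore the planned precision. Both gains are a best case: they assume that all outstanding participants are already randomised and that their control outcomes are not yet affected by opened access. Because part of the overstatement stays even then, completion alone is not a full remedy, and an adjusted estimate is needed as well.

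**What to change.** In sections 9.0 and 8.4:
- State that crossing the bound ends new randomisation and is not in itself a discontinuation of participants. Those already randomised continue the scheduled surveys and the month-6 and month-12 DBS cards, whatever PrEP service they then use.
- Keep the interim test as the efficacy decision; later data do not reopen it.
- Record the date on which any control gains access to ePrEP.

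In section 10.3, prespecify the reporting after a stop:
- the difference in proportions at the stop, with a bias-adjusted estimate and interval;
- the difference from all month-12 outcomes, once with all controls as randomised and once without control cards taken after access.

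The cost is wording in three sections. The assessments are those already scheduled in section 8.1; the documents contain no budget, so their expense after a stop cannot be judged from them. The downsides are a later final report and possible dilution of later control outcomes if the arm is opened, which the two versions of the final estimate would make visible.

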## 10.0 STATISTICAL/ANALYTIC CONSIDERATIONS

### 10.1 Introduction

10.1.1 A total of 240 participants will be enrolled at baseline to account for a 20% expected loss to follow-up during 12-months of study follow-up.

10.1.2 Primary Outcome: The primary outcome will be detectable TFV-DP drug levels at the month 12 study virtual visit based on an intention to treat analysis. Using standard pharmacological models,[17] TFV-DP level can be used to infer the mean number of days per week PrEP is ingested over a time period of approximately 1-month preceding specimen collection. The cut point used for the primary outcome measure will be TFV-DP levels considered to be a surrogate for substantial HIV protection: >700 fmol/punch, a level indicating  $\geq 4$  doses per week. The intervention efficacy measure will be quantified as the difference in proportions of the intervention arm with this outcome compared to the control arm. For the power calculations, we will therefore use a two-sample comparison of proportions.

10.1.3 Secondary Outcomes: Secondary outcome measures will be harmonized, to the extent possible, with ATN measures. Safety/tolerance outcomes will include: acute HIV symptoms, medication tolerance assessed based on side effects; adherence with number of pills taken in the past week; demographic, socio-economic, and sexual behavioral risk measures derived from the National HIV Behavioral Surveillance (NHBS) instrument and our previous research instruments;[10, 18] PrEP perceptions and PrEP use adapted from the NHBS instrument as well as other sources;[10, 19] commonly used measures for depression;[20] illicit and non-prescription drug use,[21] sexual stigma,[22] HIV severity and risk perceptions,[23] HIV knowledge,[21] medication adherence self-efficacy,[24] the systems usability scale,[25, 26] healthcare coverage,[27] and use of social and geosocial networking sites.[27] We will also seek to understand rationales for those who fail to persist in PrEP, assessing perceptions of PrEP barriers and concerns.[28, 29] The [name] Laboratory may also measure emtricitabine-triphosphate (FTC-TP), which will allow for additional study analyses regarding recency of PrEP dosing.[30]

## 10.2 Power Estimates

10.2.1 All analyses will assume 80% power to detect a difference at a two-sided 5% significance level. We will also assume a 20% attrition rate in both arms, with independent censoring. Assuming that 5% of participants in the control arm are above cut-point levels of the outcome measure (Section 10.1.2), we will have sufficient power to detect a minimum detectable effect size of 13% absolute difference in the outcome measure (e.g.  $\geq 18\%$  of participants in the intervention arm have outcome measures above the cut-point threshold). A sensitivity analysis determined that to allow for detection of a scenario where intervention outcome level = control+20% absolute increase, our study would remain sufficiently powered with any control participant uptake level  $\leq 15\%$ .

## 10.3 Statistical Analysis Plan

10.3.1 Aim 1: Analyses of primary outcome that control for potential residual confounding, and analyses of secondary outcomes including initiation of and retention in PrEP care.

Logistic regression and log-linear models will be used to estimate the association between intervention arm and the primary study outcome, TFV-DP level. If prognostic factors associated with the outcome remain insufficiently balanced through stratified randomization, we may adjust for these factors in our models. Potential confounding factors that may be included are medication self-efficacy and motivation to take PrEP. Per protocol assessments that account for potential

changes in intervention as delivered will be conducted. For instance, this would account for participants assigned to the intervention condition opting to instead receive standard of care PrEP from a non-study clinician. A number of secondary analyses will be conducted using regression models. Intervention impact on the secondary outcomes of PrEP initiation and PrEP persistence will be determined using analogous regression models. Another secondary analysis will be to model  $\log_{10}$  (TFV-DP levels) as the outcome variable. An additional secondary analysis will account for changes in PrEP eligibility over time, per CDC guidelines. This has the potential to detect significant smaller “sub-clinical” differences in adherence between the intervention and control study arms. Similarly, an analysis with FTC-TP will allow for a more sensitive and sub-clinical assessment of PrEP use. Other specific and aggregate measures of safety including: renal function, HIV incidence, and incident bacterial STI will be assessed.

**10.3.2 Aim 2: Exploratory analyses of intervention effectiveness across subgroups, and analysis of potential mediators of initiation or persistence in PrEP care across both study arms, such as self-efficacy and urbanicity.**

Heterogeneity of the intervention effects across subgroups will be explored, including that of stratification (race), and socioeconomic indicators. Understanding variables associated with success or failure in home care for PrEP will inform future research, and potentially guide clinician recommendations or policy regarding bringing PrEP to scale. For participants who seroconvert during the study, levels of TFV-DP, PrEP persistence, and other clinically-relevant study data will be analyzed.

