## 3.0 STUDY DESIGN

PrEP-naïve MSM will be recruited into the study, with a focus on Black and Latino MSM, targeted to make up half of all participants. A screening will be conducted online and involve a screening consent and questions to determine initial eligibility. This will be followed by a full consent (if eligible), a baseline survey, and the return of self-collected specimens for testing to determine clinical PrEP eligibility. Those eligible for the study will be enrolled into the trial and randomized to either intervention (ePrEP) or control (standard of care). Participants assigned to the ePrEP intervention (n=120) will have a baseline teleconsultation with a site study clinician who will be responsible for prescribing PrEP as indicated.[10] Intervention participants will be offered telemedicine consultations at 1, 3, 6, 9 and 12 months, and will complete quarterly home specimen collection for laboratory tests recommended by CDC at each time period. The study

virtual visits consist of surveys, specimen collection, and telemedicine consultation. Those assigned to the control condition (n=120) will be referred to a publicly available website that geolocates the nearest PrEP provider, [www.PrEPLocator.org](http://www.PrEPLocator.org). Both conditions will have identical TFV-DP kit collection for primary outcome assessments (6 and 12 months) and app-based surveys for secondary outcomes assessments across all study periods (baseline, 3, 6, 9, and 12 months).

The three study sites will be staffed by clinicians who will conduct telemedicine consultations and supporting staff who will address participant care needs such as referrals for treatment. Study recruitment, retention communication, and tracking will be handled by staff at the Emory University site.

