### 3.1 Study Population

A total of 240 young MSM (aged 18-29) will be enrolled and randomized into the study. All participants, at the time of screening, must live in one of the four study site states (AL, GA, MS, NC). The study will target enrollment of 50% Black or Latino MSM.

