### 3.3 Study Randomization and Stratification

An electronic data capture system (EDC) will be used to stratify randomization by site to decrease the likelihood of Type I error[11] due to the expected association between covariates and study outcome. Randomization will be accomplished within the study data management platform; within each stratum, the data system will produce a sequential block randomization list. This list will automatically populate the appropriate study arm assignment in iDataFax at the time each new participant is randomized at any of the three study sites.

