### 5.3 Randomization Procedures

Upon completion of all eligibility assessments (online behavioral screening, baseline survey and clinical), participants will be randomized to either intervention (ePrEP, n=120) or control (standard of care, n=120). Participants will be randomized using iDataFax. Randomization will be stratified by study site (AL, GA, MS, NC) to decrease the likelihood of Type I error due to the expected association between covariates and study outcome.

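### Randomisation is stratified by site, but no primary-analysis text uses the strata, no sentence fixes the final test, and the strata are three sites in 3.3 but four states in 5.3: a wording fix at no cost

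*Combined protocol and SAP*

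**What the plan says.** **Strata.** Section 5.3 says "Randomization will be stratified by study site (AL, GA, MS, NC) to decrease the likelihood of Type I error due to the expected association", which lists four levels. Section 3.3 also stratifies by site, but fills the assignment "at the time each new participant is randomized at any of the three study sites". Section 3.0 agrees with three: "The three study sites will be staffed by clinicians who will conduct telemedicine consultations". The abstract gives about 80 participants per site out of 240, which again means three. Its design line names three states, while its population line adds Alabama, and 3.1 says participants "must live in one of the four study site states (AL, GA, MS, NC". Section 10.3.2 labels race as the stratification factor, although race is a randomisation stratum nowhere.

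**Primary analysis.** Section 10.1.2 sets the effect measure: "The intervention efficacy measure will be quantified as the difference in proportions of the intervention arm with this outcome compared to the control arm". It bases the power calculation on comparing two sample proportions. Section 10.2.1 sets the level: "All analyses will assume 80% power to detect a difference at a two-sided 5% significance level". Section 9.0 names a test statistic for the interim look only, with a spending function "on the Z test statistic assuming a final alpha of 0.05 such that the interim Z statistic bounds are -2.96 and 2.96". Section 10.3.1 says "Logistic regression and log-linear models will be used to estimate the association between intervention arm and the primary study outcome, TFV-DP level". Adjustment there is optional. It applies only to prognostic factors that the stratified randomisation leaves unbalanced, and the examples are medication self-efficacy and motivation to take PrEP. Site is not mentioned.

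**The concern.** The protocol's reason for stratifying, an expected link with outcome, is also the reason to carry the strata into the analysis. The optional adjustment in 10.3.1 does not do this: stratification is meant to balance site, so a rule triggered by imbalance would leave site out.

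The deciding test also has to be inferred. Logistic and log-linear models in their usual form give odds ratios and risk ratios, not the difference in proportions of 10.1.2, and neither family is ranked above the other. With about 5 control events expected (5% of 96), reasonable tests can fall on opposite sides of 0.05 for the same data. A choice left open until outcomes are known can then affect the result.

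Finally, a stratified analysis needs a defined list of strata, and the sections do not agree on one.

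**Working it through.** **Inputs.** 120 per arm (3.2); 20% attrition, so 120 × 0.8 = 96 evaluable per arm; 5% against 18%, two-sided 5%, 80% power (10.2.1); a control rate of 15% with a 20-point increase from the sensitivity statement in 10.2.1. Site-specific rates are assumptions. All tests use a critical value of 1.96 and ignore the small alpha spent at the interim (2 × [1 − Φ(2.96)] = 0.003).

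**Step 1. Reproduce the plan's figure.** Pooled two-proportion formula, mean rate 0.115:

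n = [1.96 √(2 × 0.115 × 0.885) + 0.8416 √(0.05 × 0.95 + 0.18 × 0.82)]² / 0.13² = (0.884 + 0.372)² / 0.0169 = 93.3, so 94 per arm.

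Then 94 / 0.8 = 117.5, so 118 per arm or 236 in total, against 240 stated. Power at 96 per arm is Φ[(0.13 √96 − 0.884) / 0.442] = 81.1%. The stated 80% reproduces with an uncorrected, unstratified test. With a continuity correction, 109 per arm (137 after attrition, 274 in total) would be needed, which does not match.

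**Step 2. Tests that fit the text.** Exact enumeration of two binomials, 96 per arm:

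| Test | Size 5%/5% | Power 5% v 18% | Power 15% v 35% |
|---|---|---|---|
| Pooled Z | 4.3% | 83.8% | 90.4% |
| Likelihood ratio, binomial | 6.6% | 83.8% | 90.4% |
| Wald, logistic | 2.1% | 80.6% | 89.9% |
| Wald, log-linear | 1.6% | 80.6% | 89.5% |
| Fisher's exact | 2.0% | 76.9% | 87.5% |
| Continuity-corrected Z | 1.8% | 76.5% | 87.2% |

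The two Wald rows count tables with a zero cell as non-significant. Falling back to Z in those tables gives sizes of 3.2% and 2.6%, and power of 81.4% and 81.3% at 5% v 18%. If log-linear means Poisson regression, its likelihood-ratio test has 81.4% power at 5% v 18%. At 15%/15% the size is 5.0% for pooled Z and the binomial likelihood ratio and 4.4% for both Wald tests.

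Example: 5/96 against 13/96.
- Pooled Z: (8/96) / √(2 × 0.09375 × 0.90625 / 96) = 0.0833 / 0.0421 = 1.98, significant.
- Wald logistic: ln[(13 × 91)/(5 × 83)] / √(1/5 + 1/91 + 1/13 + 1/83) = 1.048 / 0.548 = 1.91, not significant.
- Wald log-linear: ln(13/5) / √(1/5 + 1/13 − 2/96) = 0.956 / 0.506 = 1.89, not significant.

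**Step 3. Ignoring site.** Simulation of pooled Z against CMH without continuity correction, with equal strata of m per arm. With t the events in a stratum and y those in the intervention arm, CMH is Σ(y − t/2) / √Σv, where v = m² t(2m − t) / [(2m)² (2m − 1)].

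| Assumed site rates, control to intervention | Pooled Z | CMH |
|---|---|---|
| Size, 5/5/5% | 4.3% | 4.4% |
| Size, 2/5/8% | 4.1% | 4.5% |
| Size, 5/15/25% | 4.4% | 5.0% |
| Power, 2/5/8 to 12/18/24% | 83.9% | 84.0% |
| Power, 5/15/25 to 25/35/45% | 90.9% | 91.4% |
| Power, 5/15/25 to 15/35/55% | 91.4% | 92.6% |

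With larger site differences and a common odds ratio, power is 85.0% against 86.4% (control 1/3/11%, overall 5% v 18%) and 92.5% against 94.8% (control 3/10/32%, overall 15% v 35%).

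**Step 4. Three or four strata.** With four strata of 24 per arm, Z against CMH gives 83.9% against 84.0% (2/4/6/8 to 12/16/20/24%) and 91.1% against 91.8% (5/10/20/25 to 20/30/40/50%). The number of strata hardly affects power.

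**Step 5. Test and interval are not the same procedure.** With 5% in both arms at three sites, a Wald interval for the Mantel-Haenszel risk difference rejects in about 5.7% of null trials and CMH in about 4.3%. The plan must therefore say which one decides.

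**The case against.** The strongest reply is that the final test is already implied. Section 10.1.2 fixes the endpoint, the time point, the intention-to-treat basis and the difference in proportions. Section 10.2.1 fixes the level, and 9.0 places a group-sequential boundary on a Z statistic, which would normally be carried to the final look. The heading of 10.3.1 speaks of controlling for residual confounding, close to secondary Aim 2.1 in 2.2, so its models can be read as supportive. Much of this stands, and it would be wrong to say that the plan has no discernible final test. But the default is pieced together from three sections, while the section titled as the analysis plan names other methods for the primary outcome and does not call them supportive.

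On the strata, 5.3 may list the states that three sites serve. That is plausible, but the sentence presents the four as the levels of the stratification factor, and nothing maps Alabama residents to a site.

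Two stronger readings are tempting. Since 3.3 and 5.3 justify stratification as protection against Type I error, a reader might infer that ignoring site inflates false positives; step 3 shows the reverse. A reader might also infer that the trial is underpowered; step 1 reproduces the stated power for the implied test.

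The spread of sizes in step 2 needs care. The plan names neither Wald nor likelihood-ratio tests, the lowest figure depends on how zero-event tables are counted, and at 15% the Z, Wald and binomial likelihood-ratio tests differ little in size.

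**Conclusion.** The point holds as a free improvement of modest consequence. Omitting site makes the pooled Z slightly conservative. It costs about 0 to 1 point of power in most assumed scenarios and about 2 with larger site differences. These figures rest on assumed site rates.

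The unstated test matters more. At 5% against 18%, power runs from about 77% to 83.8% across tests compatible with the text. The stated 80% is correct for the Z-type test that the plan implies, but is not secured by the wording. The conflict over strata is a matter of consistency, not of power. The documents do not support a claim of inflated Type I error, of an inadequate sample size, or of a missing primary effect measure.

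**What to change.** - In 10.3.1, name the CMH test without continuity correction, stratified by the randomisation strata actually programmed, as the single deciding test at month 12. Report the Mantel-Haenszel risk difference with its confidence interval as the estimate, and state that the CMH test governs if the two disagree.
- In 9.0, use the same stratified statistic for the interim Z.
- In 10.3.1, state that the logistic, log-linear and covariate-adjusted models are supportive, in line with Aim 2.1.
- Make the abstract, 3.0, 3.1, 3.3 and 5.3 agree on the strata, and state how Alabama residents map to sites.
- In 10.3.2, correct the label that makes race the stratification factor.

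The cost is protocol and SAP wording only: no added participants, visits or data. N = 240 stands.
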